## 1. OBJECTIVE, SPECIFIC AIMS, BACKGROUND, AND SIGNIFICANCE

### 1.1 OBJECTIVE

The primary objective of this study is to define the post transfusion recovery of fresh or stored Bio-RBCs from blood donors who carry genetic mutations that can compromise RBC function and recovery in response to ex vivo cold storage and after transfusion into subjects.

This protocol may cover up to nine () separate but similarly designed studies that may test eight groups with SNPs and a cohort of patients on testosterone replacement therapy (TRT).

The eight genetic mutations that we will evaluate may include sickle cell trait (AS), and single nucleotide polymorphisms (SNPs) in ankyrin 1 (ANK1), glucose-6-phosphate dehydrogenase X-linked (G6PD), piezo-type mechanosensitive ion channel component 1 (PIEZ01), spectrin alpha (SPTA), extended synaptotagmin-like protein 2 (ESYT2), Myo9b and SEC14. We may identify additional SNPs as our analysis of the REDS-III GWAS study advances that could replace one of these SNP groups and/or we identify additional non-synonymous SNPs that are associated with susceptibility to hemolysis of stored red blood cells. In addition, we will evaluate 15 subjects on testosterone replacement therapy with 20 controls that are gender and race matched that are not on testosterone replacement therapy.

The secondary objective is to define the effects of donors sex and testosterone replacement therapy on post-transfusion recovery and the correlation between in vitro correlates of the RBC storage lesion (e.g., storage and stress-induced hemolysis, membrane microvesicle formation) and post transfusion recovery of Bio-RBCs. This study will verify whether the negative impact of TRT on RBC storage stability observed in mice is clinically relevant in transfusion of blood from TRT donors.

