## **1.4 SIGNIFICANCE**

The quality of a unit of stored RBC for transfusion, a procedure performed about 12 million times per year in patients, is currently based on levels of storage hemolysis. However, the storage lesion is a singular manifestation of a multitude of injuries that occur during red cell storage. Hemolysis measures alone failed to capture the progressive accumulation of these changes, some of which may affect the ability of transfused red blood cells to traverse the microcirculation. Furthermore, there is limited data on the correlation between *in vitro* measures of hemolysis and post-transfusion survival of stored red blood cells. This project explores the current gaps in understanding the impact of genetic and biologic factors in blood donors on red blood cell storage stability and post transfusion recovery. We also seek to determine whether *in vitro* markers of storage integrity can predict red cell survival in the patient circulation.

Our studies in human and animal models have demonstrated that genetic variability and biological variables such as sex, age, race or iron availability may significantly modulate predisposition to hemolysis under diverse stress conditions including routine cold storage of RBC units, and in hemolytic disease. For example, we have shown that RBCs from male donors (human or mice) exhibit higher susceptibility to hemolysis during storage, and under osmotic, mechanical or oxidative stress. Furthermore, we have demonstrated the effect of donor sex, testosterone or sickle cell trait on RBC storage and post-transfusion recovery in a murine model of transfusion. As members of NHLBI REDS-III and collaborators on the RBC-Omics project, we have further demonstrated in 13,403 informed blood donors that variables such as sex, race, and donation intensity may modulate RBC hemolytic response to cold storage and to osmotic and oxidative stress. Having completed the screening of these donors for hemolytic propensity, we are currently seeking for genes that mediate hemolysis using genome-wide association approach. The biotin method would provide us the unique opportunity to verify whether our *in vitro* correlates of hemolysis or the newly discovered genes may predict RBC recovery *in vivo*.

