#### Secondary Endpoints:

- Define the 1-hour post transfusion survival of fresh or stored Bio-RBCs
- Determine the association between gender and in vitro correlates of the RBC storage lesion and post transfusion recovery of BioRBCs at selected time points (i.e. 2-4 hours, 60 days). The in vitro measurements of stored RBCs test include spontaneous cold storage hemolysis, osmotic hemolysis, mechanical fragility, AAPH-induced oxidative hemolysis, and membrane microvesicle formation. RBC predisposition to hemolysis is quantified as percent hemolysis, which accounts for the levels of RBC-derived free hemoglobin in response to cold storage (5-7 and 35-42 days following donation) or exposure of washed and stored RBCs to osmotic or oxidative stress.

**Storage hemolysis:** quantification of storage hemolysis is based on the equation:

Storage hemolysis (%) =  $\frac{(100-HCT) \times Hb_{\text{supernatant}}}{Hb_{\text{total}}}$ , for which HCT refers to the sample hematocrit (HCT),  $Hb_{\text{supernatant}}$  refers to the levels of free hemoglobin obtained after centrifugation (1500x g, 10min, 18°C) measured in the supernatant, and  $Hb_{\text{total}}$  refers to the total amount of sample hemoglobin before centrifugation.

**Stress hemolysis assays:** For the evaluation of stress-induced hemolysis, stored RBCs are washed (1500x g, 10min, 18°C) three times with phosphate-buffered saline (PBS) to remove plasma and additive solution, and immediately subjected to osmotic or oxidative stress assays.

**RBC osmotic hemolysis:** Osmotic hemolysis is determined by incubating (4h at 22°C) stored and washed RBCs in pink test buffer (a hypotonic Bis-Tris buffer containing 25mmol/L sodium chloride, 70mmol/L Bis-Tris buffer, and 135mmol/L glycerol; pH 6.6) at a final concentration of 1.6%±0.2% after which samples were centrifuged (1500x g, 10min, 18°C), and percent osmotic hemolysis is determined by: Osmotic hemolysis (%) =  $\frac{Hb_{\text{osmotic}}}{Hb_{\text{total}}} \times 100$ , for which  $Hb_{\text{osmotic}}$  corresponds to supernatant cell-free hemoglobin of pink test-treated RBCs and  $Hb_{\text{total}}$  refers to the total amount of hemoglobin of each sample.

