**RBC oxidative hemolysis:** Testing for the impact of genetic mutations on RBC susceptibility to oxidative hemolysis is performed by incubating (1.5-h, 37°C) stored and washed RBCs in the presence of 2,2'-azobis-2-methyl-propanimidamide, dihydrochloride (AAPH, 150mmol/L). After incubation, samples are centrifuged (1500x g, 10min, 18°C), and AAPH-induced oxidative hemolysis is determined by: Oxidative hemolysis (%) =  $\frac{Hb_{\text{AAPH}} - Hb_{\text{control}}}{Hb_{\text{total}}} \times 100$ , where  $Hb_{\text{AAPH}}$  corresponds to supernatant cell-free hemoglobin of AAPH-treated RBCs,  $Hb_{\text{control}}$  corresponds to supernatant cell-free hemoglobin of untreated RBCs, and  $Hb_{\text{total}}$  refers to the total amount of hemoglobin of each sample.

**Membrane microvesicle formation:** RBC-derived microvesicles will be quantified by centrifugation and collection of supernatants from stored RBC units. Microvesicles will be quantified and characterized (size) by flow cytometric analysis as described by Donadee and Gladwin.

**Correlation between primary and secondary endpoints:** We will define the associations between the primary endpoint (60-day in vivo survival of transfused Bio-RBCs) and each of those secondary endpoints by regression analysis using Pearson's r.

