### 2.5.2 Statistical Analysis

The primary assessment of RBC transfusion efficacy is post transfusion survival. Data from RBC recovery at 2-4 hours, 1 month and 2 months after each transfusion will be evaluated using mixed effect model (with restricted maximum likelihood variance estimator and bootstrapping) to calculate the effect of time, genetic group and their interaction on RBC survival. RBC recovery at each time point will be performed using the equation below.

$$\text{Percent survival (\%)} = \frac{\text{BioRBCs in circulation at } T_y \text{ (} 1 \leq y \leq 120 \text{ days)}}{\text{Baseline BioRBCs in circulation at } T_0 \text{ (20 min following RBC infusion)}} * 100$$

Secondary endpoints: The equation above will be used to define the 2-4hours post transfusion survival of BioRBCs. The other endpoints test for changes in RBC predisposition to hemolysis in cold storage by quantifying the rates of storage, osmotic, mechanical and oxidative hemolysis and the formation of RBC membrane-derived microvesicles. A sample size of 8 samples would detect a 10% difference in our assays' outputs with a power of 85%. We will use commercial software for statistical analyses (STATA version 15.0, StataCorp., College Station, Texas, USA). We will use mixed effect model (with restricted maximum likelihood variance estimator and bootstrapping) to calculate the effect of time, genetic group and their interaction on RBC survival. Normality tests will help to determine the appropriate transformation of outcome data. We will also use nonlinear term of time in these models (if applicable). We will use marginal test (from the primary models) to assess the effect of genetic group on 60-days and 2-4hours RBC survival separately. As a confirmatory analysis, Wilcoxon signed rank test will determine the differences between two groups for 60-days and 2-4 hours survival rate as well. The hypotheses will be tested primarily in old blood. A separate analysis will be performed in fresh blood transfusion as well. All P value <0.05 will be reported as statistically significant.

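### Five in vitro markers are each tested against 60-day survival with every P<0.05 called significant, unadjusted and not labelled exploratory, giving about a 13-23% chance of at least one false-positive marker

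*Combined protocol and SAP*

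**What the plan says.** - **Markers.** Protocol section 2.4, Secondary Endpoints, names five: "spontaneous cold storage hemolysis, osmotic hemolysis, mechanical fragility, AAPH-induced oxidative hemolysis, and membrane microvesicle formation".
- **Analysis.** The closing paragraph of section 2.4 relates the primary endpoint, which it describes as survival at 60 days, to "each of those secondary endpoints by regression analysis"; the statistic is Pearson's r. This sentence has one outcome time, 60 days.
- **A possible second time point.** An earlier bullet in the same list refers to gender, in vitro correlates and "post transfusion recovery of BioRBCs at selected time points (i.e. 2-4 hours, 60 days"). The sentence does not make clear whether the markers, or only gender, are to be related to recovery at both times.
- **Decision rule.** Section 2.5.2: "All P value <0.05 will be reported as statistically significant". The same section says hypotheses are tested primarily in old blood, with a separate analysis in fresh blood.
- **Status.** Section 1.1 makes the correlation of the bench markers with recovery part of the secondary objective. The synopsis also lists the marker-recovery association among the secondary endpoints. Section 1.4 adds "We also seek to determine whether" in vitro markers can predict survival in the circulation.
- **Not stated.** For these correlations there is no lead marker, testing order, multiplicity adjustment, exploratory label, sample size or power.

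**The concern.** Five tests that each carry a 5% false-positive rate, under a rule that calls any of them significant, have a joint error rate well above 5%. The plan intends to draw a conclusion from them, namely whether bench markers predict survival after transfusion. As written, that conclusion could rest on whichever of the five markers gave the smallest P value, and the report would carry no signal that it was the best of several. A marker picked out this way could be carried forward as a measure of unit quality without the support the word significant suggests.

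This is multiplicity among markers within one analysis set. It is separate from the number of genetic groups, which sections 2.4 and 2.5.1 treat as separate studies.

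**Working it through.** **The plan's own figure.** The plan gives no error rate for the marker correlations, so there is none to reproduce. Its stated power of 84% for a 13-point difference at 30 days (SD 12.5, 15 versus 20 subjects, section 2.5.1) serves to check the test convention:

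- Noncentrality = 13 / [12.5 × √(1/15 + 1/20)] = 13 / 4.27 = 3.04, with 33 degrees of freedom.
- Two-sided t-test at 0.05: power 84.0%, which matches.

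Section 2.5.2 does not say whether tests are one- or two-sided. This match supports two-sided 0.05, which is used below.

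**Inputs.**
- Markers: 5 (section 2.4).
- Outcome times: 1 (60 days) in the Pearson sentence; 2 if the bullet is read as adding 2-4 hours.
- Threshold: P<0.05 per test, unadjusted (section 2.5.2).
- Correlation among markers, and between time points: not in the documents, so assumed and varied from 0 to 0.8.
- n: 35 (15 + 20), 70 or 90 (section 2.5.1). The documents do not say whether the correlations are pooled or run within each comparison.

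**Independent tests.** Chance of at least one P<0.05 = 1 − 0.95^k.
- k = 5: 1 − 0.95^5 = 22.6%.
- k = 10: 1 − 0.95^10 = 40.1%.

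**Correlated markers.** Simulation with no true association. Pearson's r is tested by t on n − 2 degrees of freedom, so at n = 35 a result is significant when |r| > 0.334. Markers are equicorrelated. Results for n = 35:

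| Correlation among markers | 5 tests (60 days) | 10 tests, time points correlated 0.5 |
|---|---|---|
| 0 | 0.23 | 0.37-0.38 |
| 0.3 | 0.21 | 0.36 |
| 0.5 | 0.18-0.19 | 0.32 |
| 0.7 | 0.15 | 0.26 |
| 0.8 | 0.13 | 0.22 |

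Across time-point correlations from 0 to 0.8, the ten-test figure runs from 0.19 (0.8 and 0.8) to 0.40 (0 and 0). Results at n = 70 and n = 90 are nearly the same.

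**Direction.** These figures count significance either way. Counting only the direction the rationale expects (a worse marker goes with lower survival), independent tests give 1 − 0.975^5 = 11.9% for five. At correlations of 0.5, the simulation gives about 0.09 for five tests and 0.16 for ten.

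**Effect of adjusting.** Holm over five tests compares the smallest P value with 0.05/5 = 0.01, the next with 0.05/4 = 0.0125, and so on. With no true association and independent tests the error is 1 − 0.99^5 = 4.9%. It is lower when markers are positively correlated (about 0.04 at 0.5 and 0.03 at 0.8).

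**The case against.** **The count.** The only fully specified marker analysis has one outcome time, so five tests is the firm count. The bullet that mentions 2-4 hours puts gender first and can be read with gender as the predictor; the synopsis gives no time point for the marker association. This stands: ten tests is a possible reading, not an established one.

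**The size.** A reader might infer a false-positive chance of about one in three. That needs both the ten-test reading and assumed correlations of about 0.5 among markers and between time points, and the documents supply neither. Nor do they promise a 5% family-wise rate, so calling the result a multiple of a stated level would compare it with something the plan never claimed. A reader might also take every false positive as a false claim of prediction. About half would run against the plan's rationale and should invite doubt.

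**The status.** Section 2.1 calls the study a pilot, and the synopsis and section 1.4 say the project explores this gap. No stopping or go/no-go decision depends on the correlations. This limits the point to labelling and interpretation. It does not remove it: the general wording does not qualify the operative rule in section 2.5.2, and section 1.4 also speaks of prediction. Section 2.5.1 gives rare variants an analysis status of their own; nothing similar is said of the markers.

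**The choice of lead.** Storage hemolysis might seem the obvious lead marker because section 1.4 calls it the current basis for unit quality. The same section says hemolysis measures alone miss much of the storage damage. The documents therefore do not settle the choice, and it belongs to the sponsor.

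**Conclusion.** The point holds for five tests at 60 days. With no true association, the rule as written gives at least one significant marker with probability about 23% if the markers are independent, and about 13-18% at assumed inter-marker correlations of 0.8 to 0.5. If the 2-4 hour time point belongs to the marker analysis, the figure is about 20-40%.

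These values assume two-sided tests, one analysis set and equicorrelated markers, and they count both directions. Repeating the correlations in fresh blood or within each genetic comparison would add tests, but the documents do not say this will be done for the markers, so it is not counted.

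The primary comparison of genetic groups is untouched. The documents do not support a stronger inference that the marker results would be unusable: the estimates of r remain informative, and only the meaning of significant is in question.

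**What to change.** In sections 2.4 and 2.5.2, state the status of the marker-recovery correlations by one of these routes:

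1. **Exploratory (simplest).** Exclude them from the sentence that calls every P<0.05 significant, and report each r with its 95% confidence interval, labelled exploratory.
2. **Claim intended, any marker.** Apply Holm across the five 60-day tests in 35-42 day blood, which holds the family-wise error to at most about 5%. Label any 2-4 hour and fresh-blood correlations exploratory.
3. **Claim intended, one marker.** Pre-name one lead marker of the sponsor's choice, tested against 60-day survival at two-sided 0.05, with all other correlations exploratory.

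Routes 2 and 3 should not be combined without gating. A lead test at the full 0.05 plus Holm on nine others gives about 0.094 if independent and 0.086 at correlations of 0.5, not 0.05.

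The bullet with the two time points should also be reworded to say whether the markers are tested at 2-4 hours.

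The cost is wording only; no visit, sample or assay changes. The downside is that an individual marker needs a smaller P value (0.01 for the smallest of five under Holm) or carries an exploratory label.

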## 2.5 STATISTICAL ANALYSIS

### 2.5.1 Sample Size Determination

In healthy volunteers, the mean (SD) of 30 and 60-days RBC biotin recovery rate is 75% (12.5%) and 50% (10%) (calculated from 24-hour 100% recovery value), respectively. For our first study, evaluating patients with the sickle cell trait SNP, we expect SCD trait to reduce 30 and 60-day recovery to 62% and 25%. A sample size of 15 subjects with sickle cell trait (HbAS) and 20 control African American subjects (HbAA; 10 males and 10 females) would provide 84% power to detect a difference of 13% (SD =12.5%) for 30 days and a power of >95% to detect a difference of 25% (SD = 12.5%) for 60 days RBC recovery rate between AS and AA. This sample size has at least 80% power to detect the interaction between time and genetic group as measure of different recovery rate. We will also recruit an additional 20 Caucasian control (HbAA, 10 males and 10 females) to gain power for testing the effect of other RBC mutations identified in our genome-wide association studies of blood donors (NHLBI RBC-Omics). We will use explanatory analysis for the evaluation of post transfusion recovery of RBCs from subjects with rare variants (<10% of the population) due to a projected small number of subjects carrying such mutations. All 40 control subjects will be tested and selected to not have any of the SNPs that we are studying (listed below).

This power calculations informs our other planned studies that will compare up to 7 additional single nucleotide polymorphisms (SNPs) patient groups of 15 each, compared with our control groups without the SNPs (n=20 race and gender matched). Successful enrollment of the sickle trait and 7 SNP groups would be 120 total subjects. The eight genetic mutations that we will evaluate may include sickle cell trait (AS), and single nucleotide polymorphisms (SNPs) in ankyrin 1 (ANK1), glucose-6-phosphate dehydrogenase X-linked (G6PD), piezo-type mechanosensitive ion channel component 1 (PIEZ01), spectrin alpha (SPTA), extended synaptotagmin-like protein 2 (ESYT2), Myo9b and SEC14. We may identify additional SNPs as our analysis of the REDS-III GWAS study advances that could replace one of these SNP groups and/or we identify additional non-synonymous SNPs that are associated with susceptibility to hemolysis of stored red blood cells. In addition, we will evaluate 15 subjects on testosterone replacement therapy with 20 controls that are gender and race matched that are not on testosterone replacement therapy.

Each study will be conducted as an independent analysis of 15 subjects with the SNP and 20 race and gender matched subjects without the SNP using power calculations estimated from the SCD trait example above.

**Biotin infusion study:** The study team will target 70 evaluable subjects. The study team will approach 86 subjects with 90% expected to agree to yield 78 subjects who will sign the biotin infusion consent. The study team expects 90% of these subjects to complete the biotin infusion study yielding the target 70 evaluable subjects. The biotin infusion subjects include 20 Whites, 20 African American without sickle cell trait, 15 African Americans with sickle cell trait, and 15 males on testosterone. In addition, 20 subjects with SNPs from the REDS-III RBC-OMICS study will be included for a total of 98 subjects to sign the biotin infusion consent and yield approximately 90 subjects who complete the study.

REDS-III RBC-OMICs study: The study team will target 105 subjects (with SNPs) who will sign the REDS-III RBC-OMICs consent. Included in the 105 are the 20 subjects who will also sign the biotin infusion consent. In addition, approximately 40 RBC-OMICs control subjects will be tested and selected to not have any of the SNPs that we are studying. An RBC-OMICs control subject will perform the same blood draw study visit procedures at different times on the same day as an RBC-OMICs subject with one of the targeted SNPs. The study team will compare the red blood cells biophysical properties in an RBC-OMICs control subject to an RBC-OMICs subject with one of the targeted SNPs. The RBC-OMICs control subjects may be asked to return up to a maximum of 6 times in one year to perform additional optional RBC-OMICs control blood draw visits at MUH-CTRC. There will be a maximum of 6 number of blood draw visits for each of the 40 RBC-OMICs control subjects.

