	
number of single nucleotide polymorphisms (SNPs) that are associated with more red blood cell hemolysis in response to storage stress (storage, osmotic, or oxidative hemolysis). Examples of these SNPs may include sickle cell trait (AS), and single nucleotide polymorphisms (SNPs) in ankyrin 1 (ANK1), glucose-6-phosphate dehydrogenase X-linked (G6PD), piezo-type mechanosensitive ion channel component 1 (PIEZ01), spectrin alpha (SPTA), extended synaptotagmin-like protein 2 (ESYT2), Myo9b and SEC14. We hypothesize that these SNPs and others may affect the stability of red blood cells during storage and the recovery of red blood cells in the circulation after transfusion over 60 days. Additional variables that might affect red blood cell post-transfusion recovery include the donor sex and whether a donor is taking testosterone replacement therapy.
 
In general, the quality of a stored unit of red blood cells (RBC) is largely based on in vitro measures of hemolysis but the true quality of an RBC unit is based on the red cell ability to circulate through the vasculature and deliver oxygen to the tissues. Currently, there is limited data on the correlation between in vitro measures of hemolysis and post-transfusion in vivo survival of stored red blood cells. This project explores the gaps in knowledge between in vitro measures of hemolysis and in vivo lifespan of the RBC after transfusion.

Study Objectives:
	
The primary objective of this study is to define the post transfusion recovery of fresh or stored BioRBCs from blood donors who carry genetic mutations that can compromise RBC function and recovery in response to ex vivo cold storage and after transfusion into subjects.
 
The secondary objective is to define the effects of donors sex and testosterone replacement therapy on post-transfusion recovery and the correlation between in vitro correlates of the RBC storage lesion (e.g., storage and stress-induced hemolysis, membrane microvesicle formation) and post transfusion recovery of BioRBCs.

Study Hypothesis:
	
We hypothesize that genetic mutations and biologic variables (sex, race/ethnicity) in blood donors modulate the recovery of RBC after cold storage and transfusion.

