## **2.4 STUDY ENDPOINTS**

### Primary Endpoint:

The primary endpoint is the labeled red blood cell recovery rate over 60-days post transfusion (using data from 2-4 hours, 1 and 2 month) of 35-42 day stored Bio-RBCs from blood donors with specified genetic mutations, compared with control subjects without the specified mutation.

This protocol may evaluate up to eight (8) genetic mutations as independent studies, compared with pooled control groups, as well as a group of subjects on testosterone replacement therapy. The eight genetic mutations that we will evaluate may include sickle cell trait (AS), and single nucleotide polymorphisms (SNPs) in ankyrin 1 (ANK1), glucose-6-phosphate dehydrogenase X-linked (G6PD), piezo-type mechanosensitive ion channel component 1 (PIEZ01), spectrin alpha

(SPTA), extended synaptotagmin-like protein 2 (ESYT2), Myo9b, and SEC14. We may identify additional SNPs as our analysis of the REDS-III GWAS study advances that could replace one of these SNP groups and/or we identify additional non-synonymous SNPs that are associated with susceptibility to hemolysis of stored red blood cells. In addition we will evaluate 15 subjects on testosterone replacement therapy with 20 controls that are gender and race matched that are not on testosterone replacement therapy. Each group will be considered a separate study for statistical purposes. Controls will be selected based on not having any of the SNPs that will be evaluated in these studies.

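### Rare-variant SNP contrasts are non-confirmatory in one paragraph of 2.5.1 but separate, powered, 0.05-level studies elsewhere, and the planned infusions do not support that power

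*Combined protocol and SAP*

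**What the plan says.** The first paragraph of section 2.5.1 gives sickle trait its own power calculation as the first study. It then says of other variants: "We will use explanatory analysis for the evaluation of post transfusion recovery of RBCs from subjects with rare variants (<10% of the population"). The reason given is "due to a projected small number of subjects carrying such mutations". No SNP is named, and the text does not say whether the population is all donors, African Americans or the REDS-III cohort.

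The next part of 2.5.1 plans "up to 7 additional single nucleotide polymorphisms (SNPs) patient groups of 15 each" and continues: "Each study will be conducted as an independent analysis of 15 subjects with the SNP and 20 race and gender matched subjects". Those controls must be free of the variant in question, and no new power calculation is made for these groups; the sickle trait one is carried over: "using power calculations estimated from the SCD trait example above". Section 2.4 puts all the mutations under the primary endpoint: "Each group will be considered a separate study for statistical purposes". Section 2.5.2 closes with "All P value <0.05 will be reported as statistically significant". None of these three places excepts rare variants.

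The enrolment text in 2.5.1 plans 20 RBC-Omics SNP carriers for biotin infusion. They are part of the 105 SNP carriers who sign the RBC-Omics consent, which covers blood draws for in vitro testing.

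On testosterone, the Synopsis states: "The secondary objective is to define the effects of donors sex and testosterone replacement therapy on post-transfusion recovery". Section 1.1 agrees, yet section 2.4 describes the testosterone group within the primary endpoint text.

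**The concern.** I take the protocol's word explanatory to mean exploratory. On that reading, a SNP below 10% is exploratory by the first paragraph of 2.5.1 and a primary, powered comparison by the rest of 2.5.1 and by 2.4. The rule in 2.5.2 would then call its P<0.05 a significant finding. A result of, say, P=0.03 for such a SNP would be an observation or a positive primary result depending on the section followed.

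The power statement is also at stake. If the non-sickle groups are far smaller than 15, a null result will look like the outcome of a well-powered study when it is not.

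**Working it through.** **1. Status of a SNP below 10%, place by place.**
- 2.5.1, first paragraph: exploratory, because carriers are few.
- 2.5.1, paragraphs on the additional SNP groups: independent analysis, 15 vs 20, sickle-trait power.
- 2.4: primary endpoint, separate study.
- 2.5.2: P<0.05 is significant, with no exemption.

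The first entry conflicts with the other three. A SNP at or above 10% is treated consistently throughout.

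**2. The plan's own power (2.5.1: 15 vs 20, SD 12.5).** Two-sample t test, two-sided 0.05:
- SE = 12.5 × √(1/15 + 1/20) = 4.27, with 33 df and critical value 2.035.
- 30 days: noncentrality 13/4.27 = 3.04, power 84.0% (stated 84%).
- 60 days: noncentrality 25/4.27 = 5.86, power above 99.9% (stated >95%).

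The plan's figures reproduce. A one-sided test would give 90.9% at 30 days, so the stated 84% corresponds to two-sided 0.05.

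**3. Carriers needed and carriers planned.** Seven groups of 15 need 7 × 15 = 105 infused carriers; 20 are planned. An even spread gives 20/7 = 2.9 per SNP. Two full groups would need 30, so if each carrier counts towards one SNP, at most one of the seven groups could reach 15.

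**4. Power at 3 carriers, SD 12.5.**

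| Controls | SE | Noncentrality, 13 points | df | Power, 13 points | Power, 25 points |
|---|---|---|---|---|---|
| 20 | 12.5 × √(1/3 + 1/20) = 7.74 | 1.68 | 21 | 36% | 87% |
| 40 | 12.5 × √(1/3 + 1/40) = 7.48 | 1.74 | 41 | 40% | 90% |

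The 13- and 25-point differences are the sickle-trait assumptions. The plan gives no effect size for any other SNP.

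**5. Chance of at least one P<0.05 when seven SNP contrasts are all null.** Simulated with normal data, t tests at two-sided 0.05 and one shared control group:

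| Carriers per SNP | Controls | Chance of at least one |
|---|---|---|
| 15 | 20 | 24.5% |
| 3 | 20 | 28% |
| 15 | 40 | 27% |
| 3 | 40 | 29% |

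Seven independent tests would give 1 − 0.95⁷ = 30.2%.

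**The case against.** The best defence is that the rare-variant sentence is an exception and the following text the general plan: up to seven groups, each a separate study if it fills to 15, with rare variants set aside. The criterion is numerical and concerns carrier frequency, which does not depend on the recovery result. Aim 1 is worded as exploration and section 2.1 calls the trial a pilot, so the labels carry less weight than in a pivotal trial.

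Part of this stands. The exception reading is possible, and the pilot setting limits the consequences. But the exception names no SNP and no denominator, SNPs may be replaced or added as the GWAS analysis advances, and 2.5.2 still calls every P<0.05 significant.

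A reader might draw three stronger conclusions that the documents do not support:
- **That all seven other SNPs change status.** Without carrier frequencies, seven is only a ceiling.
- **That sickle trait could be reclassified too.** It is the named first study, with its own power calculation and a fixed group of 15, so the reason of few carriers does not apply.
- **That labels can be chosen freely once P values are seen.** The room for choice is limited to the undefined population and the unnamed SNPs.

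It is also fair to say that the 25 to 29% is ordinary multiplicity over seven tests, not a measure of the contradiction itself. It shows how often a significance label would arise by chance if the rule in 2.5.2 were applied to contrasts that 2.5.1 sets aside.

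**Conclusion.** The conflict is real for any SNP below the 10% threshold, and nothing in the plan resolves it. Its extent among the named SNPs is unknown.

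The power borrowed for the other SNP groups does not match the infusion plan: 84% for 13 points at 15 carriers becomes about 36 to 40% at 3. This rests on an even spread of 20 carriers over seven SNPs and on SD 12.5. A different spread changes the figure for a given SNP, but at most one group reaches 15 if carriers count once. For an effect as large as the 25 points assumed for sickle trait at 60 days, power at 3 carriers would still be 87 to 90%, so the loss matters for moderate effects.

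The 25 to 29% assumes seven true nulls, t tests and shared controls. The planned mixed model with bootstrapping could give somewhat different values.

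This should be corrected. It does not undermine the sickle trait comparison.

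**What to change.** 1. In 2.4 and 2.5.1, replace the 10% rule with a list, fixed before recovery data are seen, that names each contrast as confirmatory or exploratory.
   - Sickle trait against HbAA controls in 35-42 day stored blood is confirmatory.
   - Any SNP group that will not reach 15 infused carriers is exploratory, reported as an estimate with a 95% CI.
   - Any other SNP kept as confirmatory is named in advance.
2. Limit the significance sentence in 2.5.2 to the confirmatory list.
3. Restate 2.5.1 so that the borrowed power is claimed only for groups of 15, consistent with the 20 SNP carriers planned for infusion.
4. Separately, give the testosterone contrast one tier: it is secondary in the Synopsis and section 1.1 but sits in the primary endpoint text of 2.4.

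The cost is protocol wording, with no new subjects or procedures. The small downside is that under-filled SNP groups can no longer be reported as statistically significant. Common SNPs are not demoted by this change if their groups fill and they are named in advance.
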